4.2.2 Secondary Endpoints

Specific Aim 1

- To determine whether COMs change during standard of care treatment
- To determine whether other histological features of eosinophilic inflammation are associated with peak eosinophil counts
- To define the basic clinical and laboratory features of EG and EC.

Specific Aim 2

- To determine if specific transcripts within the EoE, EG and EC DPs are reflective of disease activity as determined by COMS.
- To compare the transcriptomes to COMs to determine which genes best correlate with specific clinical outcomes
- To determine whether patient biopsy samples can be accurately classified according to diagnosis based on their specific gene expression signatures.

4.2.3 Exploratory Endpoints

The study subjects utilized for the exploratory analyses will be the same as those recruited in Aim 1, but the exploratory study will be limited to analysis of 20 samples from each subject group with active diseases and no therapy, as well as respective control samples (tissue from subjects that have normal histology and no history of any GI disorder).

Additionally, financial resources limit performance of gene expression profiles on all patients enrolled in this study. It is important to point out that all patients will have biopsy samples collected as part of SOC and will have archived FFPE specimens available. All subjects will be given the option to donate additional biopsies for RNA analysis. So, we will be in a position to subsequently analyze specific genes in follow up validation studies and/or to test specific hypotheses that may later develop such as those about particular patient phenotypes. If the subject subsequently undergoes successful therapy, we will also assess his/her second biopsy for changes in the mRNA

transcript profile following SOC treatment. EoE, EG, and EC as well as resolution of EoE, EG, and EC will be defined as in Aim 1. Patients who consent to the procurement of an extra biopsy sample, will have two research biopsies collected in RNALater and shipped to the [name] lab. Since EG and EC are not yet well characterized, and based on our preliminary analysis that gastric tissue has minimal overlap with the EoE transcriptome, we will initially focus on taking a genome wide approach using commercial high density expression chips. As a control, we will analyze the tissue specific transcriptome for gastric and colonic biopsy tissue from subjects who underwent endoscopy for workup of EGID (EG and EC) who subsequently were found to not have EGID or other pathology and no history of prior gastrointestinal disease. The analyses will be controlled for age, gender, and other parameters. Samples will be analyzed from FFPE tissue and fresh RNA, similar to the samples from diseased tissue.

5 Study Population

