Specific Aim 2: Secondary Objective- Determine if specific transcripts within the EoE, EG and EC DPs are reflective of disease activity as determined by COMs. In this aim, we hypothesize that specific genes will correlate with and reflect EoE, EG, and EC disease activity as assessed by the COMs described in Aim 1. We will compare the transcriptomes to COMs to determine which genes best correlate with specific clinical outcomes; this will provide insight into potential pathogenic etiology of specific clinical manifestations and has the potential to predict clinical phenotypes. Preliminary studies by [name] and colleagues have interrogated the EoE-DP for its association with PEESV2.0 questions. In particular, each domain of the PEESV2.0 was correlated with the full set of genes in the EDP, using a cohort of 44 EoE patients with variable levels of esophageal eosinophils. This investigation has shown that the dysphagia domain correlated with a subset of genes. In particular, among the subset of genes were eosinophil associated genes (Charcot Leyden Crystal [CLC] and IL5Ra) and mast cell genes (carboxypeptidase A3 [CPA3]), which achieved statistically significant association. This important and potentially paradigm shifting preliminary finding highlights the proof of concept that gene expression can reflect clinical symptoms and demonstrates the ways in which we will dissect meaningful molecular-clinical data. We are well positioned to employ this innovative approach in our study since we have ready access to tissue specimens and the capabilities to perform molecular analysis, and related bioinformatics processing. Using unsupervised machine learning algorithms, we will determine whether patient samples can be accurately classified according to diagnosis based on their specific gene expression signatures. Signatures will be analyzed using a suite of gene set enrichment programs to identify metabolic pathways and/or gene networks that are enriched in these 3 rare diseases. These studies will provide preliminary data for more detailed studies focused on follow-up validation studies which will likely include studies of identified candidates as potential biomarkers of EoE, EG and EC. If our hypotheses are proven to be correct, they have potential to transform this field as we will test a number of subsequent hypotheses including 1) EoE, EG and EC are characterized by Th2 immune profiles; 2) EG and EC transcriptomes will be different than that from normal controls and 3) specific elements of the EoE, EG and EC transcriptomes will correlate with eosinophil levels (and possibly other features of inflammation). In essence, identification of the DP for each of these diseases has potential to improve monitoring of patients during therapeutic intervention and identify molecular markers with therapeutic significance.

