Biopsy slide review- This study is multi-institutional and therefore biopsies will initially be reviewed by multiple different pathologists. We will ensure the integrity of the study and minimize variability in biopsy interpretation by having a Central Review Pathology Committee (CRPC), comprised of 3 pathologists who are experts in EoE, EG and EC biopsy interpretation. We will employ slide scanning and imaging software to achieve review by the CRPC.

Archived biopsy specimens upon which the subject's diagnosis was based prior to the start of this study will be scanned or sent to the Pathology Committee. If this is not possible because the original specimen was not obtained locally or is not available in the archive, a follow up biopsy with active disease will be scanned/sent for review by the Pathology Committee. If all subsequent diagnostic biopsies are inactive due to therapy then this will be noted in the subject file at DMCC and locally.

Biopsy specimens (original diagnostic and follow up collected during enrollment in study) will be scanned or sent to the Pathology Committee for review and agreement of the diagnosis will be confirmed with the local site. If the first endoscopy during the study is the diagnostic endoscopy and diagnostic criteria is not met, the subject will be withdrawn from the study.

For a subset of 30 subjects, the histology scoring tool will be tested for inter- and intra-observer reliability at baseline and end of treatment for acceptable variability.

Pathology Evaluation Forms- Esophageal, gastric and colonic pathology forms have been developed by [name], and approved by Drs. [name] and [name], with the goal of capturing features of eosinophilia relevant to the affected tissue and also other features indicative of mucosal health and

inflammation. All 3 pathology forms will be completed on-line by a pathologist. The final forms containing one set of scores for each biopsy will be submitted for data entry following resolution of differences among the pathologists. These numerical indices of eosinophil inflammation and associated pathology will be correlated to endoscopic and symptom metrics.

Specific Aim 2

Primary Endpoints

- Disease specific transcript profiles that distinguish EG from controls and EC from controls.
- Correlation of the pattern of gene expression in each disease with tissue eosinophil level for each disease.

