5.1 Participant Inclusion Criteria

Three groups of patients will be recruited: 1) patients with an established diagnosis of EoE, EG or EC 2) patients who have a new diagnosis of EoE, EG or EC and 3) healthy controls that are having endoscopy and/or colonoscopy (this group is for the mechanistic microbiome sub-study). . . . Diagnosis of EoE is based on published criteria EG will be defined as consistent symptoms and ≥ 30 eos /HPF in 5 HPFs^{21, 23} , and EC will be defined as consistent symptoms and ≥ 65 eos/HPF²¹; in each case alternative causes of mucosal eosinophilia need to be ruled out. Inclusion and exclusion criteria and rationale are listed in Table 2. The enrollment of subjects who meet diagnostic criteria for EoE but who have not had a trial of high dose PPI will be allowed.

Following enrollment, if a subject is found to have eosinophilia in more than one site, the Pathology Committee will determine where the greatest degree of eosinophilic inflammation exists. Subjects will be categorized according to the site of greatest inflammation and the appropriate COMs for that location will be used to assess. The database will reflect that the subject has eosinophilia at multiple locations.

Table 2a- Summary of inclusion criteria for EoE, EG, EC.

Inclusion criteria	Rationale
Males or females ≥ 3 years of age;	Presence of available tools starting at this age
Presence of symptoms*#	Meets the requirement for symptoms to use PRO metrics
Mucosal eosinophilia (see below)	Essential diagnostic criterion for EoE, EG and EC
EoE- ≥ 15 eosinophils/HPF	Consensus recommendation ²
EG- ≥ 30 eosinophils/HPF in 5 HPFs	Minimum threshold ²³ and consistent with 2x Normal ²¹
EC ≥ 65 eosinophils/hpf	Minimum threshold as defined by 2x normal ²¹
MicroBiome Sub-study Controls¹	
No eosinophils on clinically indicated EGD	

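### Aim 2's within-disease gene correlations rest mainly on 20 active, untreated samples per disease, so they are range-restricted and describe variation within active disease rather than tracking of disease activity

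*Protocol*

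**What the plan says.** **Sample set.** Protocol section 4.2.3 (Exploratory Endpoints) states that the exploratory study is "limited to analysis of 20 samples from each subject group with active diseases and no therapy", together with histologically normal control tissue. Section 5.5 (Substudies) repeats the limit. Section 4.2.3 gives finances as the reason that not every patient is profiled. Section 5.5 justifies the figure of 20 by earlier work that separated disease from control.

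**Second biopsy.** Section 4.2.3 adds: "If the subject subsequently undergoes successful therapy, we will also assess his/her second biopsy for changes in the mRNA" transcript profile. No number is given, and the biopsy is not tied to any correlation endpoint.

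**Definition of active.** No count is attached to the word. Disease "as well as resolution of EoE, EG, and EC will be defined as in Aim 1". The numeric rules available there are the inclusion thresholds in section 5.1: "EoE- ≥ 15 eosinophils/HPF", "EG- ≥ 30 eosinophils/HPF in 5 HPFs", and at least 65 per HPF for EC.

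**Endpoints.** Section 4.2.1 lists as an Aim 2 primary endpoint: "Correlation of the pattern of gene expression in each disease with tissue eosinophil level for each disease". Section 4.2.2 adds secondary endpoints on whether transcripts in the diagnostic panels reflect disease activity by COMs, and on which genes correlate best with clinical outcomes. Section 12.5 tests these with Pearson or Spearman coefficients and does not say which samples enter.

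**Contrast.** Section 4.1 enrols Aim 1 subjects whatever their treatment status, because inflammation may be present or absent. It also reports preliminary gene-symptom work "using a cohort of 44 EoE patients with variable levels of esophageal eosinophils".

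**The concern.** One selection rule serves two different questions. For disease versus control, active untreated tissue gives the clearest contrast. For a correlation within a disease, the same rule removes the low end of the variable being correlated. A gene whose expression rises and falls with eosinophil load between active and resolved disease may show only a weak association among samples that are all active.

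At stake is which EG and EC genes are taken forward. Section 4.1 says the panels will be built from disease-specific genes and from those that track with features such as eosinophil level. It adds that the panels may help in monitoring patients during treatment. Correlations confined to active disease could miss or misrank such genes, and they do not cover the active-to-resolved change that monitoring concerns. EoE is less exposed: its expression profile is treated as already established, and its preliminary work covered variable eosinophil levels.

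**Working it through.** **1. The plan's own figure.** Section 12.5 states that 20 per group gives 80% power for a 2-fold difference with at most 10 false positives among 30,000 genes.

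- Per-gene alpha = 10/30,000 = 0.000333; a 2-fold difference is 1 unit on the log2 scale.
- Solving the two-sided two-sample formula for n=20 and 80% power gives a log2 SD of 0.71 (normal) or 0.65 (t).
- No SD is stated, so the figure is attainable but cannot be confirmed. It concerns a group difference only; no power is stated for the correlations.

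**2. What n=20 offers a correlation before any restriction.** By Fisher z, the detectable r at 80% power is tanh((1.960 + 0.842)/√17) = tanh(0.680) = 0.59 at two-sided alpha 0.05. It is 0.68 at alpha 0.01 and 0.79 at alpha 10/30,000.

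**3. Effect of sampling only active disease.** The documents give neither the full-range correlation nor the share of the range below threshold. Assume:

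- log eosinophil count is roughly normal over the treated and untreated range;
- 30%, 50% or 60% of that range lies below the threshold for active disease;
- the full-range correlation is r = 0.60.

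With cut-point c and active share q, let λ = φ(c)/q. The ratio of the SD in active samples to the full-range SD is u = √(1 + cλ − λ²). The restricted correlation is r′ = ru/√(1 − r² + r²u²). Power is Φ(atanh(r′)·√17 − 1.960).

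| Share below threshold | u | r′ | Power, n=20, alpha 0.05 |
|---|---|---|---|
| none (full range) | 1 | 0.60 | 82% |
| 30% | 0.70 | 0.47 | 55% |
| 50% | 0.60 | 0.41 | 44% |
| 60% | 0.56 | 0.39 | 39% |

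For the 50% row: 0.60 × 0.603/√(0.64 + 0.36 × 0.364) = 0.362/0.878 = 0.41; atanh(0.412) = 0.438; 0.438 × 4.123 − 1.960 = −0.154; Φ = 44%.

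**4. Precision.** An observed r of 0.41 with n=20 has a 95% interval of tanh(0.438 ± 1.960/√17) = tanh(0.438 ± 0.475), or about −0.04 to 0.72.

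**5. Other values of r.** With u from 0.5 to 0.8, power for a full-range r of 0.5 falls from 62% to 22-45%. For r of 0.7 it falls from 95% to 50-84%. All of these figures are for one gene, before multiplicity.

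**6. Can the second biopsies simply be pooled, with a therapy term?** Every sample in the active set is untreated, and every second biopsy follows successful therapy. A treated/untreated term is therefore aliased with resolved/active status. A simulation with r=0.60, the threshold at the median, and 20 active plus 5, 10 or 20 resolved samples treated as independent gave these approximate powers:

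- active only: 45%;
- pooled without a therapy term: 83%, 95% and 99%;
- pooled with the term: 52%, 62% and 75%.

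The term removes most of the restored range. Leaving it out lets a pure drug effect on expression appear as a correlation with eosinophils.

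**The case against.** The strongest reply is that Aim 2 is labelled exploratory and its first objective is disease versus control, which this sample suits. The limit is explained by finances, archived tissue is kept for later validation, and restricting to untreated samples avoids confounding by therapy. All of that stands. It bears on how serious the point is, but it does not make the sample match endpoints worded as correlation within disease or as reflecting disease activity. A later SAP could choose among the profiled samples, but it could not restore a range that was not sampled.

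A reader might infer several stronger points that the documents do not support:

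- **That Aim 2 profiles nothing but active, untreated tissue.** Section 4.2.3 also plans controls and second biopsies after successful therapy, and nothing expressly bars the latter from the correlations. Pooling controls would not help, because it mixes the disease-control difference into a within-disease endpoint.
- **That every sample lies above 15, 30 or 65 eosinophils per HPF.** This is a reasonable inference from the reference back to Aim 1, but it is not a stated selection rule.
- **That all these patients are symptomatic.** The rule does not require a new diagnosis, and the Table 2 footnote in section 5.2 waives symptoms for established patients. Restriction of the COM range is therefore probable rather than built in, and it is not quantified here.
- **That monitoring during therapy is a study aim.** Section 4.1 presents it as a potential benefit.

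**Conclusion.** The point holds in a limited form. The main expression set cuts the eosinophil range from below. Aim 2's within-disease correlations with eosinophil level, and probably with COMs, are therefore attenuated and imprecise, and they answer a question about variation within active untreated disease. EG and EC are mainly affected.

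On the assumed inputs, a correlation of 0.60 shrinks to about 0.47-0.39 and single-gene power falls from about 82% to 55-39%. These figures illustrate the size of the effect; the true share below threshold and the true correlation are unknown.

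It would go too far to say that the design cannot show any association. Counts above threshold still vary, and a full-range correlation of 0.7 keeps 50-84% power. Nor would a wider range cure the small sample: at n=20 the detectable correlation is still 0.59 at alpha 0.05.

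**What to change.** - Keep the 20 active, untreated samples per group for disease versus control.
- In sections 4.2.1, 4.2.2 and 4.2.3, label the correlation from those samples as correlation within active untreated disease.
- Use the second biopsies already planned in section 4.2.3 in a separate within-patient analysis that correlates change in expression with change in eosinophil count and with change in COMs. State how many pairs contribute.
- Do not rely on a single treated/untreated term in a pooled model, because it is aliased with active/resolved status. Report the paired result by type of therapy where numbers allow, and state direct drug effects on expression as a limitation.
- Limit conclusions about disease activity and monitoring to what the paired analysis supports.

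The cost is protocol wording and a little more analysis of samples already planned. The paired numbers will be small and are not fixed in advance. Pairs exist only where therapy succeeded, and some confounding by therapy will remain.

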5.1 Participant Inclusion Criteria

Three groups of patients will be recruited: 1) patients with an established diagnosis of EoE, EG or EC 2) patients who have a new diagnosis of EoE, EG or EC and 3) healthy controls that are having endoscopy and/or colonoscopy (this group is for the mechanistic microbiome sub-study). . . . Diagnosis of EoE is based on published criteria EG will be defined as consistent symptoms and ≥ 30 eos /HPF in 5 HPFs^{21, 23} , and EC will be defined as consistent symptoms and ≥ 65 eos/HPF²¹; in each case alternative causes of mucosal eosinophilia need to be ruled out. Inclusion and exclusion criteria and rationale are listed in Table 2. The enrollment of subjects who meet diagnostic criteria for EoE but who have not had a trial of high dose PPI will be allowed.

Following enrollment, if a subject is found to have eosinophilia in more than one site, the Pathology Committee will determine where the greatest degree of eosinophilic inflammation exists. Subjects will be categorized according to the site of greatest inflammation and the appropriate COMs for that location will be used to assess. The database will reflect that the subject has eosinophilia at multiple locations.

Table 2a- Summary of inclusion criteria for EoE, EG, EC.

Inclusion criteria	Rationale
Males or females ≥ 3 years of age;	Presence of available tools starting at this age
Presence of symptoms*#	Meets the requirement for symptoms to use PRO metrics
Mucosal eosinophilia (see below)	Essential diagnostic criterion for EoE, EG and EC
EoE- ≥ 15 eosinophils/HPF	Consensus recommendation ²
EG- ≥ 30 eosinophils/HPF in 5 HPFs	Minimum threshold ²³ and consistent with 2x Normal ²¹
EC ≥ 65 eosinophils/hpf	Minimum threshold as defined by 2x normal ²¹
MicroBiome Sub-study Controls¹	
No eosinophils on clinically indicated EGD	

5.2 Participant Exclusion Criteria

Table 2b- Summary of exclusion criteria for EoE, EG, EC.

Exclusion criteria	Rationale
History of intestinal surgery other than G tube placement	Can alter PRO metrics
Planned or recent enrollment in blinded investigational studies	COMs will be uninterpretable because of lack of knowledge of treatment
Esophageal stricture < 3mm	Prevents assessment of esophageal mucosa
Other identifiable causes for eosinophilia, infections, GI cancer, other GI inflammatory disease	Prevents assessment of pure subject population
Any physical, mental, or social condition, history or concurrent illness or laboratory abnormality that, in the investigator's judgment, might interfere with study procedures or the ability of the subject to adhere to and complete the study.	Could interfere with study procedures or impact subjects' ability to participate in the study.
Potential participants will be excluded if the investigator determines that the potential participant has diminished capacity and is not cognitively able to participate fully in the consenting process.	Not appropriate to enroll subjects with diminished capacity.
MicroBiome Sub-study Controls	
Use of antibiotic within 30 days of scheduled EGD	Can alter gut microbiome

*Symptoms include, but are not limited to: EoE-abdominal pain, vomiting, heartburn, feeding / eating problems, dysphagia, food impaction, EG- abdominal pain, vomiting, EC-bloody/non bloody diarrhea, tenesmus, abdominal pain

#Symptoms are not required for subjects with previously diagnosed EoE, EG, or EC. Symptoms required for new diagnoses

¹ Children and adults scheduled for a clinically indicated upper or lower GI endoscopy but not suspected to have an Eosinophilic Gastrointestinal Disorder

All diseases except for non EoE for microbiome controls will require clinical symptoms plus a minimal threshold for mucosal eosinophilia as defined in the listed references.

Participation of Women: Subjects will be recruited/enrolled without regard to sex or gender. This is a natural history study. There are no treatments involved which may pose a risk for pregnant mothers, unborn fetuses, or women who are breastfeeding. We will follow all subjects enrolled in this study. There are no requirements for birth control.

Participation of Minorities: Subjects will be recruited/enrolled without regard to racial/ethnic group.

Participation of Children: Children aged 3 years and older will be recruited/enrolled.

Co-enrollment Guidelines: If a subject enrolls in a therapeutic trial during the course of this study, COMs will not be collected during the time they are participating in the trial.

If a subject meeting criteria at the local study site does not have a confirmed diagnosis from the central review pathology committee, the subject will not continue in other OMEGA visits.

5.3 Clinical Evaluations

Subjects will be evaluated using the COMs as described in section 4.2.1. No additional clinic visits will be needed outside of standard-of-care.

